
indicating increased risk of heart failure in young patients receiving Etanercept, and certainly no data substantiating increase risk after treatment with Etanercept for a very short term course, such as two or three weeks.

In summary: the data show that Etanercept is well-tolerated with few adverse effects in a Pediatric population, and no more SAEs occur in the treatment group than the placebo group when given for several months.

Cost: Etanercept (Enbrel at \$170/25mg-vial) is inexpensive relative to cost of IVIG (pharmacy cost = \$60/gm) for the majority of KD patients.

TABLE 1. Actual pharmacy cost for IVIG versus Etanercept per patient weight.

Patient Weight (Kg)	IVIG 2 gm/kg	Enbrel – 3 (0.8 mg/kg) doses
10	\$ 1200	\$510
20	\$ 2400	\$510
30	\$ 3600	\$510

These calculations do not consider additional cost involved in readmission such as hospitalization days, IV infusion, etc.

1.4 Dose Rationale

Etanercept is slowly absorbed after subcutaneous (SC) injection, and the absolute bioavailability is approximately 58% in adults³⁷. Etanercept has a relatively small volume of distribution of 12 ± 6 and is slowly absorbed to reach its peak serum concentration about 50 hours after injection and cleared from the body with a reported median half-life of 115 hours³⁷. The recommended dosing regimen for JRA patients (4-17 years) at the time of its initial approval was 0.4 mg/kg (up to 25 mg) twice weekly by SC injection⁴⁰.

Figure 2 A. Data below is extracted from Yim et al, and shows overlay of observed and simulated data for children in JRA group receiving 0.4 mg/kg twice weekly.

[figure not shown]
[figure not shown]

Figure 2B. Data from 5 patients in pilot study receiving 0.4 mg/kg etanercept starting immediately after IVIG infusion and then weekly x 2. 1000 ng/ml = 1 mg/L

However, based on its slow absorption and elimination and pharmacokinetic (PK) profile, a doubled dose with a half-frequency regimen (ie, 0.8 mg/kg [up to 50mg]) of a once-weekly SC injection was sought and FDA approved for patient convenience. PK simulation studies using data from juvenile rheumatoid arthritis (JRA) patients receiving 0.4 mg/kg SC twice weekly show similar steady-state levels at 1 and 8 weeks for children receiving 0.8 mg/kg⁴¹. After repeated subcutaneous treatment mean serum etanercept concentration was 2100 ng/ml (range 700 to 4300 ng/ml). Although eighteen JRA patients were between age 4 and 8 years, relatively few patients were under age 5 years. The data in Figures 2 A and 3A illustrate drug concentrations from the JRA population and are extracted from Yim et al⁴¹. These can be compared to the PK profiles for the two different drug doses used in the pilot study (data shown in Figs 2B and 3B). The pharmacokinetic profiles for 5 pilot study patients, receiving 0.4mg/kg weekly (Figure 2.B), show lower than therapeutic levels, defined by 5th to 95th %tile range in shown in 2A for JRA patients receiving twice weekly doses. Steady state concentrations after 0.8 mg/kg after 1 week (Figure 3 B) are within the simulated and therapeutic range calculated for the JRA group (3A).

[figure not shown]

Figure 3A. The data extracted from Yim et al represents simulation for 0.8 mg/kg (once weekly) and 0.4 mg/kg (twice weekly). These simulations consider drug levels after 8 weeks of therapy,

These data suggest that 0.8 mg/kg weekly is adequate to maintain levels within the therapeutic range defined by the earlier JRA trials. The younger age of the KD patients does not substantially affect absorption and metabolism of etanercept. Three enrolled patients less than 2 years of age showed similar pharmacokinetic profile to all other patients and JRA patients. These patients also showed no adverse events from Etanercept.

[figure not shown]

Figure 3B shows our patient data obtained in first two weeks of etanercept treatment. We were able to maintain levels in the therapeutic range even at trough within this time period.

2 Study Objectives

Kawasaki Disease (KD) or Syndrome is the leading cause of acquired heart disease in children the United States. The Center for Disease Control estimates that over 4000 U.S. children per year are diagnosed with KD. Although, KD qualifies for Orphan Disease status by NIH and FDA standards, it is a growing and important health problem for children in the U.S. and worldwide. KD is an autoimmune disease and vasculitis with a specific predilection for coronary arteries, causing aneurysm and/or ectasia. Although, the majority of patients do well, many experience long term coronary artery abnormalities. Studies in Japan where KD demonstrates exceptionally high prevalence indicate that the mortality rate in males with coronary artery lesions is more than twice expected. Treatment with intravenous immunoglobulin and aspirin currently represent the standard of care for acute Kawasaki Disease. New and emerging data show that this treatment is only partially effective for reducing the risk of coronary artery disease. Additionally, KD in many patients demonstrates resistance or refractoriness to IVIG, and requires retreatment. This refractoriness represents a primary risk factor for development of coronary artery dilation. Attempts at developing effective adjunctive therapy for IVIG and aspirin have failed. Over the past 15 -20 years, multiple investigators have provided strong evidence implicating tumor necrosis- α (TNF- α) as a primary agent for inflammation in acute KD. TNF- α antagonism with etanercept abrogates coronary artery disease in a validated mouse model of KD. Etanercept, a dimeric fusion protein, consists of 2 molecules of the extracellular ligand-binding portion of human TNF receptor 2 attached to the Fc domain of human IgG. Etanercept is FDA approved for multiple indications in adults and in children down to four years of age for juvenile rheumatoid arthritis (JRA). We performed a pilot study in acute

CONFIDENTIAL

This material is the property of the Seattle Children's Research Institute. Do not disclose or use except as authorized in writing by the study sponsor-investigator.

KD patients (age 6 months to 5 years). In this population, we demonstrated that etanercept (0.8 mg/kg) given subcutaneously at weekly intervals in 3 doses provides concentrations within the therapeutic range defined for JRA patients. The results of the pilot study support the safety of etanercept in children and show promise for efficacy in reducing IVIG resistance.

We will test the hypothesis that TNF- α antagonism with etanercept improves the clinical response to standard of care treatment with IVIG and aspirin therapy in KD patients between 2 months and 20 years of age. To test this hypothesis we will perform a double-blinded placebo controlled trial in 196 children with KD and obtain data in order to achieve an orphan designation for etanercept.

Primary Aim

1. Determine if etanercept (0.8 mg/kg, maximum 50 mg) given subcutaneously reduces IVIG refractory rate and retreatment rate in the KD patient population. Our goal is to randomize and complete the trial in 110 patients in the etanercept treatment group and 110 patients in the placebo group.

Secondary Aims

1. Determine if the safety profile differs between the etanercept treated group and the placebo group.
2. Determine if etanercept treatment alters the rate of coronary artery dilation and disease (CAD) defined by z-scores at 2 and 6 weeks after treatment.
3. Determine the pharmacokinetics of etanercept in KD patients

3 Research Design and Methods

We propose a placebo-controlled randomized double blind multi-center study in patients, age 2 months to 20 years, with acute Kawasaki disease. All study investigators will be blinded except for pharmacists.

3.1 Primary clinical endpoint

The primary aim of this study is to determine if Etanercept (Enbrel) 0.8 mg/kg given subcutaneously to patients with acute Kawasaki Disease will reduce the incidence of IVIG refractoriness as defined in the joint American Heart Association and American Academy of Pediatrics Endorsed Clinical Report: “Refractory Kawasaki Disease will be defined as the persistence or recrudescence of fever ($\geq 38.0^{\circ}\text{C}$ or 100.4°F) at least 36 hours after the end of the IVIG infusion”³.

Rationale for primary endpoint: Refractory KD is an objective clinically important and easily measured parameter. Orphan product indications by the FDA are likely to be influenced by clinical parameters as opposed to sonographic measures. Refractoriness increases risk of coronary artery disease, number of hospitalization days and cost of treatment¹¹. Several studies have unsuccessfully used coronary artery dilation (CAD) as a primary endpoint to evaluate adjunctive therapy^{13, 14}. Risks in using CAD are: intra-observer and inter-observer variability. Although, we will have a central echocardiographic reader, subjectivity is introduced by the sonographer actually performing the study. Coronary artery dimensions can be skewed by angle, machine settings and other parameters beyond the control of the reader. Therefore, coronary artery dilation parameters will be relegated to secondary endpoints.

CONFIDENTIAL

This material is the property of the Seattle Children's Research Institute. Do not disclose or use except as authorized in writing by the study sponsor-investigator.

3.2 Secondary Clinical Endpoints

Determine if the safety profile differs between the etanercept treated group and the placebo group.

Secondary safety endpoints will be number of adverse events, serious or otherwise within 30 days of treatment, with specific focus on serious infections, defined as “those requiring hospital admission” for treatment. The latter have been noted in patients receiving much longer courses of etanercept than proposed for this protocol, and for different diseases.

Our study will be the first to evaluate efficacy of Etanercept in reducing inflammation in an acute inflammatory disease in children, as opposed to chronic inflammatory diseases. The acute phase reactant, C-reactive protein, will be followed throughout the study as a laboratory measure of inflammation. We will also determine if etanercept modifies serum concentrations of cytokines, interleukin-3, interleukin-6, and TNF- α .

We propose the largest cohort for study of Etanercept in children performed to date.

Secondary clinical endpoints will be directed to determine if etanercept treatment alters the rate of coronary artery disease defined by z-scores at 2 and 6 weeks after treatment.

We will also determine if etanercept treatment 1) alters development of coronary artery dilation or disease in patients with normal coronaries on initial echocardiogram, 2) promotes healing of coronary artery disease, when apparent on initial echocardiogram, 3) alters treatment course by reducing total number of hospitalization days, and 4) incidence of CRP normalization by 7 days.

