Features of Kawasaki Disease including vascular inflammation, high fever and marked elevation of the acute phase protein, CRP, implicate cytokines as key role players in the pathogenesis. Several cytokines are elevated in the acute phase of KD including TNF- α , interleukin-1 and interleukin-6²⁰⁻²⁴. However, TNF- α has received particular attention for several reasons. TNF- α activation of macrophages includes enhanced production and release of TNF- α receptor²⁵. Patients with KD demonstrate marked elevation in serum soluble TNF- α receptor with even higher levels in patients with coronary artery ectasia, despite IVIG treatment²⁶. Immunochemistry studies show that CD14 peripheral blood monocytes/macrophages during acute KD strongly expressed TNF- α in their cytoplasm²⁷. Expression of TNF- α weakens in the convalescent phase, suggesting that some of the intracytoplasmic granules in these monocytes/ macrophages are secretory granules, which secrete TNF- α ²⁷. TNF- α promotes migration of P-selectin and production of E-selectin promoting conformational changes in endothelium, which may promote vascular dilatation and coronary aneurysm noted in KD²⁸.

The hypothesis that TNF α promotes coronary artery inflammation is supported by data obtained in a well established mouse model of KD, created through intraperitoneal injection of *L. Casei* wall extract. These mice develop coronary artery inflammation, ectasia, and aneurysms, which histopathologically resemble coronary artery lesions seen in postmortem studies from children with KD. Coronary artery inflammation and vessel wall damage are absent in wild-type mice treated with the TNF- α receptor blocker, Etanercept (8 mg/kg twice weekly times four weeks, intraperitoneal), and in TNFR1-deficient (TNFR1 $^{-/-}$) mice²⁰. Coronary artery inflammation and ectasia does occur in mice deficient for TNFR2, which does not bind TNF- α in mice. Therefore, TNF- α plays an important role in the pathogenesis of coronary artery inflammation in this model. In summary, KD patients show activation of TNF- α pathway, and animal models show that TNF- α antagonism abrogates coronary artery inflammation.

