Etanercept, a dimeric fusion protein, consists of 2 molecules of the extracellular ligand-binding portion of human TNF receptor 2 attached to the Fc domain of human IgG1³¹. Infliximab is a chimeric IgG1 monoclonal antibody composed of human constant and murine variable regions³², whereas adalimumab is a recombinant human IgG1 monoclonal antibody³³. Each infliximab or adalimumab molecule can bind up to 2 TNF molecules; a single TNF homotrimer can bind up to 3 molecules of infliximab or adalimumab³⁴. In contrast, etanercept binds to the interface of 2 TNF subunits in a 1:1 ratio³⁵. These differences in binding avidity suggest that Etanercept may be easier to titrate according to treatment effect without inducing adverse effects or resistance. However, it is also possible that the monoclonal antibodies may be more potent and effective inhibitors of TNF. The pharmacokinetics of the drugs delivered by subcutaneous route, etanercept and adalimumab, show that blood concentration levels are subjected to less severe peaks and troughs than infliximab, delivered by intravenous infusion^{36, 37}.

In 2004, isolated case reports of infliximab use for refractory KD began to appear in the literature³⁸. Burns et al then retrospectively reviewed the experience of clinicians in the United States, who had used infliximab for KD patients with either persistent vasculitis or persistent or recrudescent fever > 48 hours after treatment with IVIG³⁹. None of these publications discuss exactly why infliximab was chosen over other TNF inhibitors. This is curious as pharmacokinetics and safety data in younger children, was and is available for Etanercept alone^{40, 41}. The retrospective analysis performed by Burns et al showed that complete response, indicated by resolution of fever, was documented in 10/16 patients³⁹. Infliximab therapy was initiated late in the disease and the majority of these patients already had coronary vasculitis prior to administration of a TNF- α blocker. One patient with severe coronary artery aneurysms preceding treatment died at home. The data from this retrospective review served as background to initiate an ongoing clinical phase I trial of infliximab versus repeat IVIG infusion for refractory KS. No information regarding the progress of this study has been published.

Etanercept for the proposed study is available and will be provided free of charge by Amgen (see supporting letter).

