5.7.4 Return or Destruction of Study Drug

Study drug that remains at the end of the study will be shipped back to Amgen, Inc or destroyed on site.

At the completion of the study, there will be a final reconciliation of drug shipped, drug consumed, and drug remaining. This reconciliation will be logged on the drug reconciliation form, signed and dated. Any discrepancies noted will be investigated, resolved, and documented prior to return or destruction of unused study drug. Drug destroyed on site will be documented in the study files.

6 Study Procedures

Etanercept 0.8mg/kg (maximum 50 mg) or placebo will be given within 48 hours of initiating IVIG infusion. Randomization will be performed by internal Pharmacy, unblinded (see Pharmacy procedures). Placebo format

CONFIDENTIAL

This material is the property of the Seattle Children's Research Institute. Do not disclose or use except as authorized in writing by the study sponsor-investigator.

will be: Etanercept placebo (Amgen), TMS Lyo, B20 UnLBL 2mL vial Pink Cap. Study schema and procedures are outlined below.

TIME	0*	12-84 hours #	7 ± 3 days	14 ± 3 days	44 ± 4 days
Physical Exam	x		x	x	X
Etanercept/Placebo	x		x	x	
PK	x	x	x	X	
Cytokines	x	x	x		
CBC^	x		x	x	X
CRP	x		x	x	X
ESR	x				
Echo	x			x	X
EKG	x			x	X
AST, ALT	x		x	x	
Albumin	x		x	x	X

* Time 0 or baseline is defined as time first dose of study drug is given. Time 0 or baseline labs are almost always done before the patient has consented to the study. These labs are optional unless the patient is qualifying into the study through supplementary lab data. In general, admission laboratory values used to confirm diagnosis of KD can be used for the study, provided that they were within 24 hours prior to initiating IVIG. If a time zero lab value is not drawn as part of the clinical course prior to the patient enrolling in the study, it will not be collected and will be recorded as missing data. After enrollment, coordinators should try to retrieve extra serum obtained along with admission laboratory studies. This serum can be used for baseline pharmacokinetic assay, PK.

An EKG is normally done at time zero as part of clinical care. This EKG is optional, if an EKG is not performed at baseline it will not be recorded as a protocol deviation.

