Adverse events will be tabulated for each treatment group by severity, relationship to study drug and body system affected (according to the NCI CTC grading and MEDDRA classification system). The outcome of any SAE episodes that occur will be summarized. Adverse event rates will be compared between treatment groups using Poisson or negative binomial regression modeling. The proportions of subjects experiencing an adverse event of any type and the proportions experiencing an SAE will be compared using chi-square or Fisher's Exact testing.

Pharmacokinetic analyses: PK analyses will be performed after completion of the study and unblinding, so as not to unblind study investigators. Samples from patients receiving etanercept will be forwarded to the Seattle site for storage and then later submitted to Amgen for determination of serum drug concentrations. Peak and trough analyses will be performed. Drug clearance, volume of distribution and $\frac{1}{2}$ life will be determined using etanercept modeling and algorithms⁴¹ and loaded on SAAM2 software available at the University of Washington.

CRP and other standard laboratory studies will be performed in the clinical laboratory of each participating hospital. Serum cytokines, IL-3, IL-6, and TNF α will be performed in Center of Developmental Therapeutics at Children's Hospital Research Institute in Seattle. Assay will be performed on Luminex-200 multiplex system, which resides in center.

8 Safety and Adverse Events

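### A between-arm difference in serum TNF-alpha would mix drug binding with any change in TNF production, and the hold that protects the blind covers PK but not cytokines

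*Combined protocol and SAP*

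**What the plan says.** **Question.** Section 3.2 (Secondary Clinical Endpoints) says "We will also determine if etanercept modifies serum concentrations of cytokines, interleukin-3, interleukin-6", with TNF-alpha completing the sentence. This comes straight after CRP, which is introduced as the laboratory marker of inflammation.

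**Sampling.** The schedule table in Section 6 has the row "Cytokines x x x", with marks at time 0, 12-84 hours and day 7 ± 3. There is no cytokine mark at day 14 or day 44, although blood is taken at both visits. The footnote says "Time 0 or baseline is defined as time first dose of study drug is given" and, of time-0 laboratory tests, "These labs are optional unless the patient is qualifying into the study through supplementary lab data". Section 6.2 makes the 12-84 hour visit optional.

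**Drug and analyte.** Section 1.2 says that "etanercept binds to the interface of 2 TNF subunits in a 1:1 ratio". Section 1.4 reports that after repeated dosing in juvenile rheumatoid arthritis "mean serum etanercept concentration was 2100 ng/ml (range 700 to 4300 ng/ml". It adds that in the Kawasaki pilot, levels over the first two weeks stayed within the range it treats as therapeutic, trough included.

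**Assay and hold.** Section 7 places the cytokine assays at the Seattle research institute on a Luminex-200 multiplex system. It does not say whether free, bound or total TNF is read, plans no check for drug interference, and gives no date and no statistical method for cytokines. For PK the same section says "PK analyses will be performed after completion of the study and unblinding, so as not to unblind study investigators".

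**The concern.** Etanercept works by binding TNF, and only one arm receives it. If the assay's reading depends on whether TNF is bound, the arms can differ with no change in TNF production. A larger sample or adjustment for baseline would not remove this, because the effect travels with treatment. At stake is a mechanistic statement, that etanercept raised or lowered TNF, in data that Section 2 says are meant to support an orphan designation.

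The blinding issue follows from the same fact. An assay that responds to the presence of drug can hint at allocation. The plan guards against this for PK but is silent for cytokines. The blind matters here because the primary outcome in Section 7 includes a clinical decision to retreat with IVIG.

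**Working it through.** The plan gives no figure of its own to reproduce on this point. There are three checks.

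**1. Is drug present at every post-baseline cytokine draw?**

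Inputs from Section 1.4: peak about 50 h after injection, median half-life 115 h, bioavailability 58%, volume of distribution 12 ± 6 (no unit given; litres assumed). A 50 mg dose, the protocol maximum, is used with these adult values. The model has one compartment with first-order absorption.

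- k = ln 2 / 115 = 0.00603 per h.
- ka solves ln(ka/k)/(ka − k) = 50, giving ka = 0.0472 per h.
- f(t) = [ka/(ka − k)] × [exp(−kt) − exp(−ka·t)]; concentration = 0.58 × 50 mg / 12 L × f(t).

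Plausibility: the average at weekly dosing is 0.58 × 50 / (0.00603 × 12 × 168) ≈ 2.39 mg/L, or about 2,390 ng/mL. The cited mean is 2,100 ng/mL, so the order of magnitude is right.

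| Draw, after first dose only | Share of first-dose peak | Concentration, ng/mL |
|---|---|---|
| 12 h | 56% | about 1,000 |
| 84 h | 91% | about 1,620 |
| day 4 | 85% | about 1,520 |
| day 7 | 56% | about 1,005 |
| day 10 | 37% | about 650 |

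With a volume of 6 to 18 L, the day 10 value runs from 1,304 to 435 ng/mL. Drug is present throughout both windows. The time-0 sample is normally taken before dosing, but it cannot show a treatment effect.

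The day 44 visit has no cytokine draw. At nominal days it falls 30 days (720 h, 6.26 half-lives) after the last dose, when 2^(−6.26) ≈ 1.3% of drug would remain.

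**2. How large is the excess?**

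The documents give no serum TNF level and no molecular masses. Assumed: 150 kDa (drug), 51 kDa (TNF), and TNF of 10 to 10,000 pg/mL.

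- Drug at 700 ng/mL: 700 µg/L ÷ 150,000 g/mol ≈ 4,667 pM.
- TNF at 10 pg/mL: 10 ng/L ÷ 51,000 g/mol ≈ 0.196 pM; ratio ≈ 23,800.
- TNF at 10,000 pg/mL: ≈ 196 pM; ratio ≈ 24.
- Drug at only 300 ng/mL with TNF at 10,000 pg/mL: 2,000 / 196 ≈ 10.

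Under these assumptions there is enough drug to bind the TNF present. The calculation does not show how much is bound or how the assay reads bound TNF.

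**3. Can cytokine results reach blinded staff?**

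- Section 3 requires all investigators except pharmacists to be blinded.
- Section 7 holds PK only.
- Section 10.6 lists analyses of primary and secondary endpoints among the Session Report contents, and also laboratory values. The laboratory item follows the baseline item and may mean baseline only; the endpoint item carries no such limit. Cytokines sit under the secondary-endpoint heading of Section 3.2.
- Section 10.4 has the study coordinator prepare these reports and makes them available to everyone at the DMC meeting. Investigators may join the Open Sessions.
- Section 10.3 sets meetings at least every 6 months.

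The route exists on paper. The outline does not say whether results appear by arm or by patient.

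**The case against.** The strongest reply is that interference is not documented. The platform is named but the kit is not, so the assay might read a well-defined form of TNF. This stands in part. A reader might infer that TNF results are worthless, or that the arms are certain to be measured on different analytes. The documents do not support either reading. They show that the drug binds TNF and is present; they do not show how the assay responds or in which direction. What remains is that the plan offers no means of separating binding from production.

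A reader might also take a large molar excess as established. It is not: the TNF levels and masses are assumed, and the 700 to 4,300 ng/mL range comes from arthritis patients after repeated dosing, whereas both cytokine windows centre on the first dose.

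Cytokines appear in no numbered aim in Section 2, and Section 7 plans no cytokine test. This stands, and it limits the severity.

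On blinding, it can be said that no early cytokine assay is scheduled, and that PK needs its own hold because only active-arm samples are forwarded for assay. Both are true. A reader might infer that cytokines will be assayed during the trial and will unblind the coordinating site; nothing in the documents says so. The gap is silence, combined with Session Reports that could carry the results.

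Finally, Section 1.1 says "Several cytokines are elevated in the acute phase of KD including" TNF-alpha, interleukin-1 and interleukin-6, so a reader might fault the panel for measuring IL-3 rather than IL-1. Section 1.2 answers this: the three analytes chosen are those reported to fall under etanercept in other inflammatory diseases.

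**Conclusion.** The point holds for TNF-alpha only. As planned, a between-arm difference in TNF-alpha combines drug binding with any change in production. It should not be presented as an anti-inflammatory effect unless the assay is shown to measure a defined form, free or total, in the presence of etanercept. That drug is present at every post-baseline draw rests on the protocol's own PK statements, and the model agrees with them. The excess of roughly 24-fold to 23,800-fold at 700 ng/mL rests on assumed TNF levels and masses. IL-6, IL-3 and CRP are outside this objection.

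The blinding point holds as a gap in wording: the protection given to PK is not extended to an assay that may also respond to drug.

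Neither part touches the primary analysis. This is a cheap improvement of minor severity.

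**What to change.** - In Section 7, base the cytokine treatment comparison on IL-6 and IL-3, and state the method, since none is given.
- Report TNF-alpha by arm descriptively, with no treatment-effect claim, unless recovery in etanercept-spiked serum shows which form the assay measures. If it does, name that form wherever the result is reported.
- Extend the PK hold to cytokines: run them in one batch after database lock and keep the results out of the Session Reports described in Sections 10.4 and 10.6.

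The cost is the loss of a TNF treatment-effect claim, a small amount of assay checking, and storage of the cytokine samples until lock. Visits, blood draws and sample size do not change.
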